### Part I: Physical activity

15I.1. How often do you perform moderate to vigorous physical activity for at least 10 minutes that makes you breathe harder/break into a sweat?

- 4 times a week or more  
 1-3 times a week  
 Never

15I.1.1. How many hours per week would you spend performing these physical activities?

- Less than 2.5 hours per week  
 2.5 hours per week or more

15I.2. LS7 Activity score

\_\_\_\_\_

15J. Total LS7

\_\_\_\_\_

Note: Score out of 14.

### Section 16: Stroke risk by the Stroke Riskometer App (Baseline only)

16.1. Risk assessment date

\_\_\_\_\_

16.2. Riskometer assessment done by

- CRA    HWC    Participant

16.3. Father or mother had a stroke or heart attack before reaching the age of 65.

- Yes    No    Unknown

16.4. 5- year Stroke risk (%)

---

16.5. 5- year Relative risk (%)

---

16.6. 10- year Stroke risk (%)

---

16.7. 10- year Relative risk (%)

---

### Section 17. Health Service Use (3, 6, 9 and 12 months)

17.1. Have you visited your GP since your stroke/TIA  Yes  No

17.1.1. If Yes, how often since your TIA/stroke?

Once  
 Twice  
 Three times  
 Four times  
 More than 4 times  
 Can't remember

17.2. Have you visited your GP since the last assessment  Yes  No

17.2.1. If Yes, how frequently have you visited your GP?

Once  
 Twice  
 Three times  
 Four times  
 More than 4 times  
 Can't remember/unknown

17.3. Have you received other healthcare services since your stroke/TIA?  Yes  No

17.3.1. Which services have you received?

visiting nurses  
 speech therapy  
 psychologist  
 physiotherapy  
 social worker  
 counsellor  
 occupational therapist  
 other health provider (e.g. neurologist)  
 other

17.4.1. For the above services, how many visits did you receive per week?  1  2  3  4  
 5 or more

17.4.2. For the above services, how many visits did you receive per week?  1  2  3  4  
 5 or more

17.4.3. For the above services, how many visits did you receive per week?  1  2  3  4  
 5 or more

17.4.4. For the above services, how many visits did you receive per week?  1  2  3  4  
 5 or more

17.4.5. For the above services, how many visits did you receive per week?  1  2  3  4  
 5 or more

17.4.6. For the above services, how many visits did you receive per week?  1  2  3  4  
 5 or more

17.4.7. For the above services, how many visits did you receive per week?  1  2  3  4  
 5 or more

17.4.8. For the above services, how many visits did you receive per week?  1  2  3  4  
 5 or more

17.4.9. For the above services, how many visits did you receive per week?  1  2  3  4  
 5 or more

17.5. Have you received other healthcare services since the last assessment ?  Yes  No

17.5.1 If Other, please state \_\_\_\_\_

17.6 Have you received other healthcare services since the last assessment  Yes  No

17.7 State what other services you have received \_\_\_\_\_

17.8.1 Have you received any personal care/home help since your last assessment?  Yes  No

17.9.2 How often have you received home help?  
 Daily  
 2 to 3 times per week  
 once a week  
 once a fortnight  
 once a month or less

17.10.1 Do you receive any other type of help?  Yes  No

17.11.2. State what other help you receive. \_\_\_\_\_

17.12 Has there been a change in your employment status since your TIA/stroke?  Yes  No

17.12.1 What changes have occurred since your last assessment?  
 Newly employed  
 No longer employed  
 Reduced hours  
 Changed job or type of work  
 Now self-employed  
 Other

17.12.2 Please explain answer to 17.12.1 \_\_\_\_\_

---

17.13 Are you currently in paid employment?  Yes  No

---

17.13.1. If Yes to 17.13., what number of hours have you usually worked in the past 2 weeks? \_\_\_\_\_

---

17.14. Are you currently paying for any private health or support services?  Yes  No

---

17.14.1. If Yes to 17.14, what services? \_\_\_\_\_

# C - Contact Details

Participant Registration Number \_\_\_\_\_

**TIIPS**

# Trial of an Individualised Intervention for the Prevention of Stroke

## 1. Contact Information

'This form is for TIIPS [registration\_number].'

1.3 Title

\_\_\_\_\_

1.4 First name(s)

\_\_\_\_\_

1.4.1. Preferred Name

\_\_\_\_\_

1.5 Last name

\_\_\_\_\_

---

1.6 Address

---

---

1.7 Email address

---

---

1.8 Home phone number (including area code)

---

---

1.9 Work phone number (including area code)

---

---

1.10 Mobile phone number

---

---

1.11. Preferred Phone number

Home phone    Work phone  
 Mobile phone

---

1.12. Preferred day/time to receive follow up call.

Weekdays    Weekends  
 Mornings    Afternoons  
 Evenings

---

1.13. Any other preferential information ?

---

---

1.14. How would participant like to receive the information sheet?

Post    Email    Text

---

1.15. Has the study manager checked the receipt of the information sheet?

Yes    No

---

## 2. Post Discharge Contact

---

2.1. Are the contact details after discharge from hospital different from above ?

Yes    No

---

2.1.1. First name(s)

---

---

2.1.2. Last name

---

---

2.1.3. Address

---

---

2.1.4. Phone Number

---

---

2.1.5. Mobile Number

---

**3. Alternate Contact (friend or relative)**

3.1 First name(s)

\_\_\_\_\_

3.2 Last name

\_\_\_\_\_

3.3. Address

\_\_\_\_\_

3.4. Home phone number (including area code)

\_\_\_\_\_

3.5. Work phone number (including area code)

\_\_\_\_\_

3.6. Mobile phone number

\_\_\_\_\_

3.7. Email address

\_\_\_\_\_

**3.a. Alternate Contact 2 (friend or relative)**

3.1a First name(s)

\_\_\_\_\_

3.2a Last name

\_\_\_\_\_

3.3a. Address

\_\_\_\_\_

3.4a. Home phone number (including area code)

\_\_\_\_\_

3.5a. Work phone number (including area code)

\_\_\_\_\_

3.6a. Mobile phone number

\_\_\_\_\_

3.7a. Email address

\_\_\_\_\_

**4. General Practitioner**

4.1 Title

\_\_\_\_\_

4.2 First name(s)

\_\_\_\_\_

4.3 Last name

\_\_\_\_\_

4.4. Name of GP practice

\_\_\_\_\_

4.5. Address

\_\_\_\_\_

4.6. Work phone number (including area code)

\_\_\_\_\_

4.8. Email address

\_\_\_\_\_

## R - Randomization

Participant Registration Number \_\_\_\_\_

**TIIPS**

# Trial of an Individualised Intervention for the Prevention of Stroke

On the date that participant's demographics were recorded, the age of the participant (in years) was: \_\_\_\_\_

From the age calculated above, please select the age bracket (in years) that the participant falls into:

- 18-54
- 55-75
- The participant falls outside of the required ages of 18-75 years

Sex

- Male
- Female

Ethnicity

- NZ Euro
- Maori
- Pacific
- Asian
- MELAA
- Other

Please randomize the participant now into either the HWC group or the UC group, now that their age, sex and ethnicity has been entered.

- HWC - Group A
- UC - Group B

## F - Follow Up

Participant Registration Number \_\_\_\_\_

### Section 3: Initial Assessment

3.1. Which assessment is this? (tick one only)

- 3 months
- 6 months
- 9 months
- 12 months

3.1.1. Did the assessment take place?

- Yes
- No
- Unknown

3.1.2. If no, please choose the appropriate response.

- Withdrawn
- Not contactable
- Unwell/deceased
- Other (specify)

3.1.2.1 Specify

\_\_\_\_\_

3.2. Date of assessment

\_\_\_\_\_

---

3.2.1 Place of assessment

- AIH North Clinic    AUT South Campus
- AUT City    Participant Home
- Phone assessment    Via video
- Other (specify)

---

3.2.2 If Other, please specify

---

---

**Section 7: Montreal Cognitive Assessment**

**MONTREAL COGNITIVE ASSESSMENT (MOCA)**  
Version 7.1 Original Version

NAME :  
Education :  
Sex :

Date of birth :  
DATE :

**VISUOSPATIAL / EXECUTIVE**

Copy cube

Draw CLOCK (Ten past eleven)  
(3 points)

POINTS

[ ]
[ ]
[ ]
[ ]
[ ]

Contour
Numbers
Hands
\_\_\_/5

**NAMING**

[ ]

[ ]

[ ]

\_\_\_/3

**MEMORY** Read list of words, subject must repeat them. Do 2 trials, even if 1st trial is successful. Do a recall after 5 minutes.

	FACE	VELVET	CHURCH	DAISY	RED	
1st trial						No points
2nd trial						

**ATTENTION** Read list of digits (1 digit/ sec.). Subject has to repeat them in the forward order [ ] 2 1 8 5 4  
Subject has to repeat them in the backward order [ ] 7 4 2

\_\_\_/2

Read list of letters. The subject must tap with his hand at each letter A. No points if  $\geq 2$  errors  
[ ] FBACMNAAJKLBAFAKDEAAAJAMOF AAB

\_\_\_/1

Serial 7 subtraction starting at 100 [ ] 93 [ ] 86 [ ] 79 [ ] 72 [ ] 65  
4 or 5 correct subtractions: **3 pts**, 2 or 3 correct: **2 pts**, 1 correct: **1 pt**, 0 correct: **0 pt**

\_\_\_/3

**LANGUAGE** Repeat : I only know that John is the one to help today. [ ]  
The cat always hid under the couch when dogs were in the room. [ ]

\_\_\_/2

Fluency / Name maximum number of words in one minute that begin with the letter F [ ] \_\_\_\_ (N  $\geq$  11 words)

\_\_\_/1

**ABSTRACTION** Similarity between e.g. banana - orange = fruit [ ] train - bicycle [ ] watch - ruler

\_\_\_/2

**DELAYED RECALL**

Has to recall words WITH NO CUE	FACE	VELVET	CHURCH	DAISY	RED	Points for UNCUE recall only
	[ ]	[ ]	[ ]	[ ]	[ ]	

\_\_\_/5

**Optional**

Category cue	FACE	VELVET	CHURCH	DAISY	RED
Multiple choice cue					

**ORIENTATION** [ ] Date [ ] Month [ ] Year [ ] Day [ ] Place [ ] City

\_\_\_/6

© Z.Nasreddine MD

[www.mocatest.org](http://www.mocatest.org)

Normal  $\geq 26 / 30$

TOTAL \_\_\_/30

Administered by: \_\_\_\_\_

Add 1 point if  $\leq 12$  yredu

((Upload the image of printed and completed MoCA for this participant.))

7.1.1. Visuospatial/Executive score

\_\_\_\_\_

7.1.2. Naming score

\_\_\_\_\_

7.1.3. Attention score

\_\_\_\_\_

7.1.4. Language score

\_\_\_\_\_

7.1.5. Abstraction score

\_\_\_\_\_

7.1.6. Delayed Recall score

\_\_\_\_\_

7.1.7. Orientation score

\_\_\_\_\_

7.1.8. MoCA total score

(If MOCA  $\leq$  25, the participant is not eligible for the study.)

Cognitive Impairment WARNING !!!!

## Section 8. Hospital Anxiety and Depression Scale (HADS)

**Please indicate which of the following options best describes how you have been feeling during the last week.**

8.1. I feel tense or wound up

- Most of the time  
 A lot of the time  
 From time to time, occasionally  
 Not at all

8.2. I still enjoy the things I used to enjoy

- Definitely as much  
 Not quite as much  
 Only a little  
 Hardly at all

8.3. I get a sort of frightened feeling as if something awful is about to happen

- Very definitely and quite badly  
 Yes, but not too badly  
 A little, but it doesn't worry me  
 Not at all

- 
- 8.4. I can laugh and see the funny side of things
- As much as I always could
  - Not quite so much now
  - Definitely not as much now
  - Not at all
- 
- 8.5. Worrying thoughts go through my mind
- A great deal of the time
  - A lot of the time
  - From time to time, but not too often
  - Only occasionally
- 
- 8.6. I feel cheerful
- Not at all
  - Not often
  - Sometimes
  - Most of the time
- 
- 8.7. I can sit at ease and feel relaxed
- Definitely
  - Usually
  - Not often
  - Not at all
- 
- 8.8. I feel as if I am slowed down
- Nearly all the time
  - Very often
  - Sometimes
  - Not at all
- 
- 8.9. I get a sort of frightened feeling like 'butterflies' in the stomach
- Not at all
  - Occasionally
  - Quite often
  - Very Often
- 
- 8.10.. I have lost interest in my appearance
- Definitely
  - I don't take as much care as I should
  - I may not take quite as much care
  - I take just as much care as ever
- 
- 8.11. I feel restless as if I have to be on the move
- Very much indeed
  - Quite a lot
  - Not very much
  - Not at all
- 
- 8.12. I look forward with enjoyment to things
- As much as I ever did
  - Rather less than I used to
  - Definitely less than I used to
  - Hardly at all
- 
- 8.13. I get sudden feelings of panic
- Very often indeed
  - Quite often
  - Not very often
  - Not at all
- 
- 8.14. I can enjoy a good book or TV programme
- Often
  - Sometimes
  - Not often
  - Very seldom

---

8.15. Anxiety Score (Sub Total)

(Advise the participant and study manager to contact GP if the score is equal to or more than 11.)

---

Anxiety warning

---

8.16. Depression Score (Sub Total)

(Advise the participant and study manager to contact GP if the score is equal to or more than 11.)

---

Depression warning

---

8.17. Has the mental health record form sent to the GP?

Yes  No

---

Upload Mental Health Record Form.

---

Any comments.

---

8.18. Have all the screening questions been completed?

Yes  No

---

If NO, please complete all screening questions before proceeding.

---

### Section 9: Comorbidities.

9.1. Does the participant have any of the following? (tick all that apply, if previously ticked it won't display again)

- Previous TIA
  - Elevated blood lipids (cholesterol),
  - Hypertension (elevated blood pressure)
  - Type 1 diabetes
  - Type 2 diabetes
  - Coronary artery disease, angina
  - Previous irregular pulse (arrhythmia), atrial fibrillation,
  - Valvular heart disease,
  - Heart failure,
  - Peripheral vascular disease (pain in legs when walking),
  - Epilepsy/seizures
  - Migraine,
  - Previous head injury (resulting in loss of consciousness),
  - Patent Foramen Ovale defect (PFO)
  - Renal/kidney disease,
  - COPD (obstructive cardiopulmonary disease)
  - Cancer
  - Arthritis
- 

9.1.1. If yes to TIA, add the date

---

9.2. Have you experienced any significant stress in the last year?

Yes  No

---

9.2.1. If YES, please rate your level of stress over the last 2 weeks (0= No stress; 10 = extremely stressed)

\_\_\_\_\_

9.2.2. Please comment in case the participant wants to share the reason e.g. bereavement.

\_\_\_\_\_

9.3. Have you experienced memory problems in the past year?

Yes  No

9.4 Have you ever been diagnosed with COVID19?

Yes  No

Date of diagnosis for COVID?

\_\_\_\_\_  
(approximate date acceptable)

How was the diagnosis done?

- Home RAT test  
 PCR test  
 Unknown (medical records only)

### Section 10: Current Medications.

10.2. CVD Medications prescribed at discharge (Tick all that apply)

- Aspirin  
 Dipyridamole  
 Clopidogrel  
 Warfarin  
 Dabigatran  
 Rivaroxaban  
 Blood pressure lowering medication(s)  
 Lipid lowering therapy (statins)  
 Diabetes medication(s),  
 Mood modification therapy  
 Oral contraceptives  
 Supplements (herbal or vitamins)  
 Other  
 None of the above  
 (Complete Section 11 only if medications medications are taken (Q10.1))

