## 9. AIMS AND HYPOTHESES

### 10. PRIMARY AIM

The **primary aim** is to determine the effectiveness of HWC in improving blood pressure at 6 months post-randomisation.

The primary hypothesis is that HWC initiated one-month post ( $\pm$  two weeks) of the onset of first-ever in a lifetime minor stroke or onset of TIA will lead to clinically meaningful improvements in lifestyle behaviours resulting in a mean difference of 6 mm Hg change in blood pressure from Baseline to 6 months post-randomisation in the HWC compared to usual care. Recurrent TIA onset is included.

The primary end-point is the difference in the mean change from Baseline in systolic blood pressure at 6 months post-randomisation between UC and HWC. The study is powered to detect a mean difference in change of 6 mm Hg ( $SD \pm 20$  mm Hg) between HWC and UC groups at 6 months post-randomisation.

---

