Blood pressure	SBP ≥ 140 mm Hg or DBP ≥ 90 mm Hg	SBP 120–139 mm Hg or DBP 80–89 mm Hg or treated to goal	SBP < 120 mm Hg and DBP < 80 mm Hg
Blood glucose	≥ 126 mg/dL	100–125 mg/dL or treated to goal	< 100 mg/dL

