## The Life's Simple 7 scale

Table 3. Definitions of the LS7 categories \*

Life's Simple 7	Level of Cardiovascular Health		
	Poor	Intermediate	Ideal
Lifestyle Factors			
Body mass index, kg/m 	≥30	25.0–29.9	<25
Physical activity, min/day	0 MVPA	>0 – <150 MPA or MVPA >0 to <75 VPA	≥150 MPA or MVPA ≥75 VPA
Healthy diet score	0–1 components	2–3 components	4–5 components
Cigarette smoking	Current	Quit <12 months ago	Never or quit >12 mo
Medical risk factors			
Blood pressure, mmHg	≥140/≥80	120 – 139/80–89 or <120/<90 with med	<120/<80 no med
Total cholesterol, mg/dL	≥240	200–239 or <200 with medication	<200
Fasting blood glucose, mg/dL	≥126	100–125	<100
Glycosylated Hemoglobin, %	≥6.5 or taking diabetes med	5.7–6.4	<5.7

M, moderate; V, vigorous; PA, physical activity.

(i) Fruits and vegetables ≥4.5 cups/day; (ii) Fish 3.5-oz servings (preferably oily fish) ≥2 servings/week; (iii) Sodium <1500 mg/day; (iv) Sweets/sugar-sweetened beverages ≤450 kcal (36 oz)/week; (v) Whole grains (1.1 g of fiber in 10 g of carbohydrates), 1-oz-equivalent servings ≥3 servings/day.

\*Note: Fasting blood glucose in mmol/l is ≥7.00 (poor), 5.55–6.99 (adequate) and <5.55 (optimum). Plasma total cholesterol, mmol/l ≥ 6.22 (poor), 5.18–6.21 (adequate) < 5.18 (optimum).

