## 31. SECONDARY END POINTS

Secondary outcomes include: (1) difference in the mean change in the LS7 scale score at 6 months post-randomisation between UC and HWC (2) the change in individual lifestyle components of the LS7 scale (BMI, smoking, physical activity, and diet) at 6 and 12 months; (3) diastolic BP (mmHg); (4) quality of life (EQ-5D-5L), (5) awareness of stroke risk factors and warning signs, (6) medication adherence (7) cognitive outcomes (8) adverse events including hospitalisations; and (9) health service use and costs.

The LS7 scale includes BP, cholesterol, blood glucose, BMI, smoking, physical activity, and diet. The score of LS7 will be calculated by providing 2 points for ideal, 1 point for intermediate, and 0

points for poor status of each of the 7 individual factors. Ideal levels of health factors were: non-smoker or quit >1 year ago; BMI <25 kg/m^2; BP <120/80 mm Hg; total cholesterol <200 mg/dL; fasting blood glucose <100 mg/dL; ≥150 min/week of physical activity; and a healthy diet score (≥4 components). Study participants who were treated to target levels for hypercholesterolemia, hypertension, or diabetes mellitus were classified as intermediate for the respective health factor. Thus, the LS7 summary score will range from 0 to a maximum of 14 points, with a higher score indicating healthier status.

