## 40. APPENDIX C CASE RECORD FORMS

### List of TIIPS study case record forms

	Form Name	Purpose
1	Form A NHI number	Confidential record of NHI number
2	Form B Baseline and Screening	Screening for eligibility, and Baseline demographic and health related information
3	Form C Contact Details	Record of participant contact details, alternate contact and GP contact
4	Form F Follow-up	Follow-up assessments at 3, 6, 9 and 12 months
5	Form R Randomisation	Completion of data entry for randomisation, and record of group allocation
6	Form S Serious adverse events	Record of stroke/TIA/MI recurrent events, death and hospitalisation
7	Form Z Coaching assessment and compliance	Record of coaching sessions, compliance, and assessment of coaching quality

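### The follow-up form asks for medications prescribed at discharge, not those being taken, so as printed the 6-month LS7 score cannot use current treatment status

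*Protocol*

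**What the plan says.** The list of case record forms in Appendix C gives the purpose of Form F as "Follow-up assessments at 3, 6, 9 and 12 months". On that form the medication section is headed "Section 10: Current Medications", and the item beneath it reads "10.2. CVD Medications prescribed at discharge (Tick all that apply". Form B, used at baseline, has the same heading and item. Both forms then carry the instruction "Complete Section 11 only if medications medications are taken (Q10.1", but Section 10 starts at 10.2 on each, and no item 10.1 is printed.

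The LS7 rules depend on treatment. Section 31 states "Study participants who were treated to target levels for hypercholesterolemia, hypertension, or diabetes mellitus were classified as intermediate for the respective health factor". Table 2 in Section 20 makes blood pressure intermediate at "SBP 120–139 mm Hg or DBP 80–89 mm Hg or treated to goal", and has the same provision for treated participants under cholesterol and glucose. Table 3 reserves the ideal blood pressure category for "<120/<80 no med" and places cholesterol below 200 mg/dL on medication in the intermediate category. Each factor scores 2, 1 or 0. The change in LS7 at 6 months is the first-listed secondary endpoint in Section 31.

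**The concern.** Discharge from the index admission comes before randomisation, so a follow-up question about discharge prescriptions asks for the same unchanging fact at every visit. It cannot show that a participant has since started or stopped a drug. The 6-month LS7 score needs exactly that for blood pressure and cholesterol, and for glucose under some of the protocol's rules.

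Two things are at stake. The first is correct scoring of LS7 for participants whose treatment changed. The second is a description of co-treatment beside the primary result. Section 10 (Primary aim) says coaching "will lead to clinically meaningful improvements in lifestyle behaviours resulting in a mean difference of 6 mm Hg change in blood pressure", and a reader of that result will want to know how antihypertensive use stood in each arm at 6 months. An analysis plan cannot restore a field that was not collected.

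**Working it through.** No sample size, power or error-rate figure enters this point, so there is no stated figure to reproduce. The check compares the forms with the scoring rules and then does simple arithmetic for scale.

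**1. Is current treatment recorded elsewhere in the printed follow-up forms?**
- Form F, Section 11 (SEAMS and items 11.14 and 11.15): confidence in taking medicines and trouble remembering them. No drug or class is recorded.
- Form F, Section 15 (LS7): readings and scores. Items 15A.9, 15B.6 and 15C.2 do not name the medication field that feeds the score.
- Form F, Section 17: visits, services and employment. No medicines are recorded.
- Form S: admissions, vascular events and deaths.
- Table 1: lists SEAMS but no measure of current medication.

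The discharge list is therefore the only printed source of treatment status at 6 months.

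**2. When does the score go wrong?**
- Started after discharge, value in the ideal range: recorded as untreated, scored 2 instead of 1. Error +1.
- Stopped after discharge, value in the ideal range: recorded as treated, scored 1 instead of 2. Error −1.
- Blood pressure in the intermediate or poor numerical range: the category is the same with or without treatment. Error 0.
- Treatment status unchanged since discharge: error 0.

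For blood pressure the reach is narrow. Form B stops enrolment when average systolic pressure is below 130 mm Hg, and the ideal range is below 120. An affected participant must have fallen by more than 130 − 120 = 10 mm Hg. Cholesterol has no such entry limit.

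For glucose the rules disagree. Table 2 and Section 31 make treated participants at target intermediate. Table 3 gives fasting glucose no medication rule and places people taking diabetes medication in the poor category for glycosylated haemoglobin. Whether a glucose error arises depends on which rule applies.

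**3. Scale**

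For one factor, the shift in the LS7 contrast = 1 point × (net misclassified share in HWC − net misclassified share in usual care), where net share means over-scored minus under-scored. The documents give no figure for these shares, so the range is assumed:
- difference of 5 percentage points: 1 × 0.05 = 0.05 points
- difference of 10 percentage points: 1 × 0.10 = 0.10 points

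For comparison, Section 6 gives the previous coaching trial's LS7 means. The contrast is (7.39 − 7.08) − (7.15 − 7.15) = 0.31 points. The assumed shifts are 0.05/0.31 = 16% and 0.10/0.31 = 32% of it.

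**The case against.** The strongest reply is that Form F points to a question on medications being taken, Q10.1, which may exist in REDCap even though it is not printed. A reader might infer from the printed form that treatment changes after randomisation are never captured. The documents do not establish that; they show only that no printed item captures them. The reply stands to that extent, and the sponsor should confirm what Q10.1 holds. If it is only a yes/no gate to Section 11, it would not supply drug classes and the gap would remain.

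A reader might also infer that the primary endpoint is compromised. It is not. Section 30 defines it as the between-arm difference in mean change in systolic pressure. That pressure is measured directly, and the intention-to-treat contrast is valid without medication data. Section 11 lists adherence to CVD medication among the secondary aims, so a drug change after randomisation may be one route by which coaching works and need not be balanced between arms.

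A third inference is that the LS7 error favours coaching. The session outline in Section 24 mentions referrals but has no medication module, and the advice to seek care for high readings (Appendix A) is given at study visits without distinction by arm. A differential change is possible, but its direction is not documented.

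Finally, Form F carries other baseline text unchanged, such as the eligibility stops after the MoCA and blood pressure items. This points to uncorrected copying and not to a deliberate choice. That explains the error but does not remove it.

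**Conclusion.** The point holds as a data-capture error on a printed form. The heading and the item in Section 10 of Form F contradict each other, and as printed the form does not capture treatment status at follow-up. The 6-month LS7 score is then wrong by 1 point per factor for participants whose blood pressure or cholesterol medication started or stopped after discharge and whose value is in the ideal range. Glucose may be affected too, once Table 2 and Section 31 are reconciled with Table 3.

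This rests on two assumptions: that the discharge list feeds the LS7 score, since the form prints no other source, and that Q10.1 does not record drug classes. The between-arm effect is unknown in size and direction, and the 0.05 to 0.10 points are illustrative only. For the primary endpoint, all that is lost is the description of co-treatment beside the result.

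**What to change.** On Form F, reword item 10.2 to *CVD medications currently taken (at this assessment)* and keep the same tick list. Print Q10.1 or delete it, and correct the instruction that opens Section 11 accordingly. State that treatment status for the 6-month LS7 score comes from the reworded item, and reconcile the glucose medication rule across Table 2, Section 31 and Table 3. Tabulate current antihypertensive use by arm at 6 months beside the systolic pressure result.

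Recording changes in dose or number of agents is optional, because LS7 scoring needs only treated or untreated status. The cost is one reworded REDCap item and about a minute per contact. The change should be made before more follow-up visits take place, since status missed at a visit may not be recoverable.
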